8.7. Analysis of Primary Endpoints

Primary endpoint data will be summarized by cohort, disease criteria, treatment, and overall across disease criteria (i.e., Overall CST103/CST107 and Overall Placebo) using the FAS. Selected summaries may be repeated in the PPS. All data will be listed.

Informal differences between CST103/CST107 and placebo may be assessed for primary endpoints. For continuous endpoints, the difference is defined as CST107/CST107 minus placebo. Comparisons may be made using a mixed model with factors for disease criteria, treatment, treatment sequence, subject nested in sequence (as a random effect), period, and baseline values as appropriate. Comparisons between treatments may also be compared using the paired t-test and/or nonparametric tests where appropriate.

Additional analyses may be performed and will be described in the SAP.

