#### 4.3. Sample Size Considerations

A total of approximately 40 subjects is planned in this crossover study. The sample size for the study parts are based on practical considerations. No formal hypothesis testing is planned.

The crossover design allows for an increased level of precision in estimates as compared to a parallel design with the same number of subjects. For primary and cognition related secondary endpoints, a sample size of 20 subjects in each cohort provides at least 80% power in this cross-over design to detect a treatment difference of  $0.79*SD$  (active versus placebo) or larger for each endpoint of interest, where SD represents the standard deviation for the endpoint of interest.

For cognition related secondary endpoints, a sample size of 40 subjects overall (both cohorts combined) provides at least 80% power in this cross-over design to detect a treatment difference of  $0.54*SD$  (active versus placebo) or larger for each endpoint of interest. Sample size assumptions were based on a 2-sided t-test with a Type I error rate of 5%, equal (or no) carryover effects, and a correlation of at least 0.3 between study periods. No adjustments were made for dropouts or multiplicity.

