- ATT Difficulty Multiplier Mean (Phase 2B): The mean of the difficulty multiplier calculated over the entire 2B assessed phase of the task. This measure is only calculated during the times that either ‘Finger/Lift’ and/or ‘Multi-touch’ are not occurring. The measurement name for this parameter in the files downloaded from the CANTAB portal is ATT2BDM.
- ATT Difficulty Multiplier Standard Deviation (Phase 2B): The standard deviation of the difficulty multiplier calculated over the entire 2B assessed phase of the task. This measure is only calculated during the times that either ‘Finger Lift’ and/or ‘Multi-touch’ are not occurring. The measurement name for this parameter in the files downloaded from the CANTAB portal is ATT2BDSD.
- SST Stop Signal Reaction Time: The estimate of time where an individual can successfully inhibit their responses 50% of the time. This covert measurement is sampled from the length of time between the go stimulus and the stop stimulus at which the subject is able to successfully inhibit their response on 50% of the trials. We can infer that this is the time before which all actions become ballistic and the subject is no longer able to cancel their action selection. The measurement name for this parameter in the files downloaded from the CANTAB portal is SSTSRT.
- SST Median RT: All Go Trials: The median reaction time taken across all the valid Go trials in the task. The measurement name for this parameter in the files downloaded from the CANTAB Portal is SSTMRTG.

In addition to the descriptive statistic summaries for the above, for each parameter, a mixed effects model approach will be used to evaluate treatment effect. The model will include change from baseline as the dependent variable, baseline as a covariate, treatment sequence, period, timepoint (i.e, Day 1: 4 hrs post-dose, Day 7: 4 hrs post-dose, Day 14: 4 hrs post-dose), disease type, and treatment as fixed effects, and subject as a random effect. The least square means will be summarized, as well as the least square mean difference between treatments, where the

Sponsor: CuraSen Therapeutics, Inc.  
Protocol Number: CST103/CST107-CLIN-011  
Version and Date: [REDACTED] v1.0 / 24May2022

corresponding p-value for this LS mean difference will be provided. All inferential analyses are exploratory in nature given that this study was not powered based on any statistical assumptions.

Line plots detailing individual subject results of the ATT parameters will be produced.

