### *Verbal Fluency Test*

The 'ALPHABET' and 'CATEGORY' tests from the Brief and Simple Index of Cognition (BASIC) tests are used in this study. For the ALPHABET task, subjects are given one minute to say aloud as many words they can think of that begin with the letter F, avoiding repetitions or the same words with different endings. The total score is the number of correct words generated. For the CATEGORY task, subjects are given 1 minute to say aloud as many animals they can think of, avoiding repetitions. The total score is the number of animals generated.

Similar to the CANTAB data, descriptive summaries for the ALPHABET and CATEGORY total scores (identified in the raw data as AAACCPT and CAACCPT, respectively) and change from baseline will be provided at each collection timepoint (i.e, Day 1: 4 hrs post-dose, Day 7: 4 hrs post-dose, Day 14: 4 hrs post-dose), and a mixed effects model with change from baseline as the dependent variable, baseline as a covariate, treatment sequence, period, timepoint, disease type, and treatment as fixed effects, and subject as a random effect. The LS mean, LS mean difference, and p-value for the difference will be reported.

Verbal fluency data will be listed on the FAS.

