Heart Rate Variability (HRV) is computed for each activity period using two methods, LF/HF which is a ratio of low frequency to high frequency and RMSSD which is the root mean square of the successive differences. For each of the 8 metrics below, a set of descriptive statistics is computed (coefficient of variation, minimum, maximum, mean, 5th, 25th, 75th, 95th percentiles, standard deviation), and the mean of each parameter will be assessed using the mixed modeling described later on:

  - Sleeping HRV LF\_HF (identified in the raw data as hrv\_lfhf\_sleeping).
  - Sleeping HRV RMSSD (identified in the raw data as hrv\_rmssd\_sleeping).
  - Resting HRV LF\_HF (identified in the raw data as hrv\_lfhf\_resting).
  - Resting HRV RMSSD (identified in the raw data as hrv\_rmssd\_resting).
  - Moving HRV LF\_HF (identified in the raw data as hrv\_lfhf\_moving).
  - Moving HRV RMSSD (identified in the raw data as hrv\_rmssd\_moving).
  - Waking HRV LF\_HF (identified in the raw data as hrv\_lfhf\_wake).
  - Walking HRV RMSSD (identified in the raw data as hrv\_rmssd\_wake).
- Temporal pedometry:
  - Average Gait Cadence as defined as steps per minute during walking (identified in the raw data as avg\_gate\_cadence).
  - Step Count Rate as defined as step counts per hour during periods classified as walking (identified in the raw data as step\_count\_rate).

If a subject has at least 5 days of sensor wear within each period, the metrics will be aggregated for each period to obtain a single value. Descriptive statistics of the 17 metrics noted above, as well as the 7 activity metrics noted in Section 8.1 above, and change from baseline will be reported for both Cohort A and Cohort B subjects. A mixed model with change from baseline period as the dependent variable, baseline period value as a covariate, treatment sequence, post-baseline period (i.e., 1, 2), disease type, and treatment as fixed effects, and subject as a random effect will be analyzed for these posture, sleep, autonomic function, activity tracking, and temporal pedometry parameters for all subjects and LS means, LS mean differences, and p-values will be presented.

*Epworth Sleepiness Scale (ESS)*

Sponsor: CuraSen Therapeutics, Inc.  
Protocol Number: CST103/CST107-CLIN-011  
Version and Date: █████ v1.0 / 24May2022

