The ESS is an 8-item, self-administered questionnaire in which subjects are asked to rate, on a 4-point scale (0-3), their usual chances of dozing off or falling asleep while engaged in 8 different activities. The total score is the sum of the 8 item scores, with scores ranging from 0 (no daytime sleepiness) to 24 (high sleep propensity in daily life). The ESS will be administered on Day 1 (Baseline), Day 7, and Day 14 of each treatment period. Descriptive statistics of total scores and change from baseline will be reported. Additionally, a mixed model will be used to evaluate the treatment effect. The model will include change from baseline as the dependent variable, fixed effects for baseline, treatment sequence, period, timepoint (i.e., Day 7, Day 14), disease type, and treatment, and a random subject effect. LS mean, LS mean difference, and LS mean difference p-value will be reported.

ESS data, including responses to individual questions, will be provided in a listing.

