#### *Pupillary Diameter*

Summary statistics of the observed values (averages by occasion) and change from baseline for the parameters listed in Section 8.1 (INIT, END, ACV, MCV, ADV, T75) will be reported. In addition, to assess the treatment difference between CST-103/CST-107 and placebo, a mixed model with baseline, treatment sequence, period, timepoint (i.e., Day 1: 4 hrs post-dose, Day 7: 4 hrs post-dose, Day 14: 4 hrs post-dose), disease type, and treatment as fixed effects, and a random subject effect, will be analyzed, with the LS mean, LS mean difference, and p-value for the LS mean difference will be reported for each pupillometry parameter noted above.

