#### *Geriatric Depression Scale (GDS)*

The GDS is a 30-item self-administered yes/no question test constructed for brief screening of depression in elderly persons. Total scores are the summation of scored responses (responses indicating worsening depression equate to 1, and responses indicating lessening depression equate to 0) from each question. Scores greater than 9 are considered suspect for depression. The GDS will be administered on Day 1 (Baseline), Day 7, and Day 14 of each treatment period. Summary statistics of total scores and change from baseline will be presented. A mixed model with change from baseline as the outcome, baseline as a covariate, fixed effects for treatment sequence, period, timepoint (i.e., Day 7, Day 14), disease type, and treatment, and subject as a random effect will be analyzed. LS mean, LS mean difference and its associated p-value will be reported.

All GDS data, included responses to individual questions, will be listed.

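### Five SAP mixed models use two or three visits per period with subject as the only random effect, so treatment p-values are too small if visits within a period correlate more than visits across periods

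*SAP*

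**What the plan says.** SAP section 8.2 gives each secondary measure its own mixed model for change from baseline and reports a least squares mean difference with a p-value. Five of these models use more than one post-baseline visit per period:

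- CANTAB, 16 key measures, three visits (Days 1, 7 and 14): "and treatment as fixed effects, and subject as a random effect".
- Verbal fluency, two scores, the same three visits: "timepoint, disease type, and treatment as fixed effects, and subject as a random effect".
- Pupillometry, six parameters, the same three visits: "disease type, and treatment as fixed effects, and a random subject effect, will be analyzed".
- ESS, one score, two visits: "timepoint (i.e., Day 7, Day 14), disease type, and treatment, and a random subject effect".
- GDS, one score, two visits: "disease type, and treatment, and subject as a random effect will be analyzed".

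Neither document names a subject-by-period effect, a residual covariance structure, a robust standard error or a degrees-of-freedom method for these models. Protocol section 8.7, which section 8.8 carries over to the secondary endpoints, lists "subject nested in sequence (as a random effect), period, and baseline values as appropriate" among its factors and has no timepoint factor. The SAP added the repeated visits without a variance term to go with them.

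Two models are not affected. HADS has only Day 14 after baseline, and for BioStamp "the metrics will be aggregated for each period to obtain a single value".

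**The concern.** In this crossover a subject's treatment is constant within a period, so the treatment comparison is a comparison of two periods per subject. Three visits in one period do not give three independent looks at that comparison if they share something that belongs to the period, such as the subject's state in those two weeks.

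A random subject intercept alone forces the same correlation on every pair of a subject's visits, whether or not they fall in the same period. Any extra likeness within a period goes into the residual and is divided by the number of visits as if it were independent noise. Visits at most two weeks apart are likely to be more alike than visits on either side of a washout of at least 14 days, although the documents give no figure for this.

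The trial looks for a signal in one of many measures, and SAP section 5.3 makes no Type I error adjustment. In this SAP, FERT, EEG and PK analyses go to separate plans and the Cohort B primary data are listed only. Most of the treatment p-values that the SAP itself produces therefore come from the models in section 8.2. Standard errors that are too small give extra false signals and confidence intervals that are too narrow.

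**Working it through.** **1. The plan's own power figures.** SAP section 4.3 gives a two-sided 5% t-test and "a correlation of at least 0.3 between study periods". The SD of a within-subject difference is SD × √(2 × (1 − 0.3)) = 1.183 SD.

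- n = 20, 0.79 SD: noncentrality 0.79 × √20 / 1.183 = 2.99, power 80.8% (19 df) or 80.6% (18 df).
- n = 40, 0.54 SD: noncentrality 0.54 × √40 / 1.183 = 2.89, power 80.4% or 80.3%.

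Both figures reproduce. They use one value per subject per period.

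**2. True and reported standard errors, without a baseline covariate.** Let rb and rw be the between-period and within-period correlations, with total variance 1 and m visits per period. The subject-by-period variance is rw − rb and the visit error variance is 1 − rw.

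- True variance of the treatment difference: 2 × [(rw − rb) + (1 − rw)/m] / n.
- Variance reported by the subject-only model: 2 × MSE / (n × m), with expected MSE = (1 − rw) + m × (rw − rb) × (n − 2) / [n(2m − 1) − (m + 1)].

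Take n = 40, rb = 0.3 (the SAP's minimum) and rw = 0.5 (assumed):

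- m = 3. True: 2 × (0.2 + 0.5/3)/40 = 0.01833, SE 0.135. Reported: MSE = 0.5 + 3 × 0.2 × 38/196 = 0.616, and 2 × 0.616/120 = 0.01027, SE 0.101. Ratio 0.75, rejection about 14%.
- m = 2. True: 2 × (0.2 + 0.5/2)/40 = 0.0225, SE 0.150. Reported: MSE = 0.5 + 2 × 0.2 × 38/117 = 0.630, and 2 × 0.630/80 = 0.01575, SE 0.126. Ratio 0.84, rejection about 10%.

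**3. The SAP model simulated, with its baseline covariate.** REML fits, no treatment effect, complete data, 2,000 runs per cell (Monte Carlo SE 0.5-0.9 percentage points). Fixed effects were the period's own baseline, sequence, period, timepoint, disease type and treatment, with random subject. Rejection rate of a nominal 5% test:

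| Visits | Between / within correlation | n = 20 | n = 40 |
|---|---|---|---|
| 3 | 0.3 / 0.4 | 9.5% | 9.3% |
| 3 | 0.3 / 0.5 | 12.9% | 12.4% |
| 3 | 0.3 / 0.7 | 17.9% | 16.2% |
| 3 | 0.5 / 0.6 | 10.9% | 12.3% |
| 3 | 0.5 / 0.7 | 15.0% | 15.4% |
| 3 | 0.7 / 0.8 | 14.9% | 15.7% |
| 2 | 0.3 / 0.5 | 9.4% | 8.7% |
| 2 | 0.3 / 0.7 | 11.7% | 12.4% |
| 2 | 0.5 / 0.6 | 9.8% | 8.8% |
| 3 | 0.3 / 0.3 | 6.1% | 5.4% |
| 3 | 0.5 / 0.5 | 6.8% | 6.6% |
| 3 | 0.7 / 0.7 | 8.6% | 9.0% |

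With three visits the ratio of model SE to true SE is 0.78 at 0.3/0.5 and 0.79-0.81 at 0.5/0.6. A second simulation (3,000 runs per cell, without the disease factor) gave 13.2% and 12.8% at 0.3/0.5 with three visits, and 9.9% and 10.0% with two. At n = 40 the critical values of the two models hardly differ, so the inflation comes from the standard error and not from the degrees of freedom.

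**4. Expected false signals.** Three-visit measures: 16 + 2 + 6 = 24. Two-visit measures: 2. With valid tests, 26 × 0.05 = 1.3. At 0.3/0.5 and n = 20: 24 × 0.129 + 2 × 0.094 = 3.3. At 0.5/0.6: 24 × 0.109 + 2 × 0.098 = 2.8 (n = 20) and 24 × 0.123 + 2 × 0.088 = 3.1 (n = 40).

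**5. With a subject-by-period term.** Tested on n − 3 df as an approximation to Kenward-Roger, rejection is 3.5-6.5% in every cell of the first simulation and 4.5-5.9% in the second.

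**The case against.** **The SAP does not rule out a residual covariance structure.** A programmer could add one. That is true, but nothing in the plan requires it, and the model as listed gives the inflated rates. A choice left open until programming is not pre-specified.

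**The size rests on assumed correlations.** This stands. The 0.3 is a minimum used for sample size and not an estimate, and pairing it with 0.7 gives the largest figures in the table. The rows with a gap of 0.1 are the more cautious guide, and they still show 9-16% with three visits. Applying one pair of correlations to all 26 measures is a simplification.

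**The analyses are exploratory, and no primary analysis is touched.** This limits the consequence. With 26 independent valid tests the chance of at least one p < 0.05 is already 1 − 0.95^26 = 74%, so no single result could be read as confirmatory. But leaving multiplicity unadjusted is a declared choice that a reader can allow for, and a standard error about 20% too small is not visible to the reader.

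**Equal correlations are not fully safe either.** Rejection reaches about 9% at 0.7/0.7. Every visit in a period shares the same baseline, and the single fitted baseline slope carries part of that baseline's error into all of them. This makes the problem somewhat wider than the within-versus-between condition alone.

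**Differences by visit are a matter of taste.** Descriptive summaries by visit are already planned, so a model-based display by visit is optional.

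**Conclusion.** The concern holds. The five models, their visit counts and their single random effect are as the SAP states them, and their treatment standard errors are too small whenever visits within a period correlate more than visits across periods. The direction is firm. The size is conditional: with three visits, about 9-18% rejection for a nominal 5% test over the correlations examined, and with two visits about 9-12%. At 0.3/0.5 or 0.5/0.6 that is roughly three false signals among 26 null measures where 1.3 are expected.

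These figures assume complete, balanced data, a baseline taken within each period, and within-period correlations that the documents do not supply. Because the analyses are secondary and exploratory, this should be fixed, but it does not undermine the trial.

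**What to change.** In the CANTAB, verbal fluency, ESS, pupillary diameter and GDS paragraphs of SAP section 8.2, add a random subject-by-period effect beside random subject and name Kenward-Roger degrees of freedom. An equivalent is a within-period residual covariance in addition to random subject. HADS and BioStamp need no change.

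Optionally, for CANTAB, verbal fluency and pupillometry, add a treatment-by-timepoint term as a supportive display and show the difference with its 95% interval at Day 1, Day 7 and Day 14. The single pooled difference mixes a first-dose visit with the two later ones. It can remain the main summary: the protocol's dose rationale expects cognitive effects after one dose, and pooling is more precise if the effect is constant.

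The cost is one sentence in each of five paragraphs and a few lines of SAS. Intervals widen: in the three-visit simulations the model SE rises about 28-31% at 0.3/0.5 and 0.5/0.6. At 0.3/0.3, where the term is hardly needed, it rises about 7-8% and the test becomes slightly conservative (about 4%). Estimates by visit are less precise than the pooled one.

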### *Verbal Fluency Test*

The 'ALPHABET' and 'CATEGORY' tests from the Brief and Simple Index of Cognition (BASIC) tests are used in this study. For the ALPHABET task, subjects are given one minute to say aloud as many words they can think of that begin with the letter F, avoiding repetitions or the same words with different endings. The total score is the number of correct words generated. For the CATEGORY task, subjects are given 1 minute to say aloud as many animals they can think of, avoiding repetitions. The total score is the number of animals generated.

Similar to the CANTAB data, descriptive summaries for the ALPHABET and CATEGORY total scores (identified in the raw data as AAACCPT and CAACCPT, respectively) and change from baseline will be provided at each collection timepoint (i.e, Day 1: 4 hrs post-dose, Day 7: 4 hrs post-dose, Day 14: 4 hrs post-dose), and a mixed effects model with change from baseline as the dependent variable, baseline as a covariate, treatment sequence, period, timepoint, disease type, and treatment as fixed effects, and subject as a random effect. The LS mean, LS mean difference, and p-value for the difference will be reported.

Verbal fluency data will be listed on the FAS.

### *BioStamp (AUS/NZ Subjects Only)*

In addition to activity tracking/classification, the BioStamp nPoint device will continuously track posture (classifications, durations, and temporal patterns), sleeping patterns (duration, posture, transitions, and activity counts), autonomic function (heart rate variability (HRV)), and temporal pedometry via daily step count and gait cadence. There are 29 daily metrics calculated by the BioStamp device related to posture, sleeping patterns, autonomic function, and temporal pedometry. These metrics are then aggregated by study period (Baseline period, Treatment Period 1, Treatment Period 2).

- Posture:
  - Percent Resting Time defined as the percentage of waking time spent resting (sum of lying, sitting, and standing) (identified in the raw data as resting\_percent).
  - Percent Lying Time defined as the percentage of waking time spent lying (identified in the raw data as resting\_lying\_percent).
  - Percent Sitting Time defined as the percentage of waking time spent sitting (identified in the raw data as resting\_sitting\_percent).
  - Percent Standing Time defined as the percentage of waking time spent standing (identified in the raw data as resting\_standing\_percent).

- Percent Upright Posture defined as the percentage of resting time when the patient's posture was classified as upright. All time not classified as upright is classified as leaning (identified in the raw data as upright\_posture\_percent).
- Sleeping patterns:
  - Average Sleep Duration as defined by average hours of sleep for days that include sleep periods (identified in the raw data as avg\_sleep\_duration).
  - Average Sleep Posture Transitions as defined by the average number of sleeping posture transitions that occur per hour during sleep (identified in the raw data as sleeping\_posture\_transitions\_rate).
  - Sleeping Activity Counts as defined by activity counts per hour during sleeping periods (identified in the raw data as activity\_sleeping).
- Autonomic function:

Heart Rate Variability (HRV) is computed for each activity period using two methods, LF/HF which is a ratio of low frequency to high frequency and RMSSD which is the root mean square of the successive differences. For each of the 8 metrics below, a set of descriptive statistics is computed (coefficient of variation, minimum, maximum, mean, 5th, 25th, 75th, 95th percentiles, standard deviation), and the mean of each parameter will be assessed using the mixed modeling described later on:

  - Sleeping HRV LF\_HF (identified in the raw data as hrv\_lfhf\_sleeping).
  - Sleeping HRV RMSSD (identified in the raw data as hrv\_rmssd\_sleeping).
  - Resting HRV LF\_HF (identified in the raw data as hrv\_lfhf\_resting).
  - Resting HRV RMSSD (identified in the raw data as hrv\_rmssd\_resting).
  - Moving HRV LF\_HF (identified in the raw data as hrv\_lfhf\_moving).
  - Moving HRV RMSSD (identified in the raw data as hrv\_rmssd\_moving).
  - Waking HRV LF\_HF (identified in the raw data as hrv\_lfhf\_wake).
  - Walking HRV RMSSD (identified in the raw data as hrv\_rmssd\_wake).
- Temporal pedometry:
  - Average Gait Cadence as defined as steps per minute during walking (identified in the raw data as avg\_gate\_cadence).
  - Step Count Rate as defined as step counts per hour during periods classified as walking (identified in the raw data as step\_count\_rate).

If a subject has at least 5 days of sensor wear within each period, the metrics will be aggregated for each period to obtain a single value. Descriptive statistics of the 17 metrics noted above, as well as the 7 activity metrics noted in Section 8.1 above, and change from baseline will be reported for both Cohort A and Cohort B subjects. A mixed model with change from baseline period as the dependent variable, baseline period value as a covariate, treatment sequence, post-baseline period (i.e., 1, 2), disease type, and treatment as fixed effects, and subject as a random effect will be analyzed for these posture, sleep, autonomic function, activity tracking, and temporal pedometry parameters for all subjects and LS means, LS mean differences, and p-values will be presented.

*Epworth Sleepiness Scale (ESS)*

Sponsor: CuraSen Therapeutics, Inc.  
Protocol Number: CST103/CST107-CLIN-011  
Version and Date: █████ v1.0 / 24May2022

The ESS is an 8-item, self-administered questionnaire in which subjects are asked to rate, on a 4-point scale (0-3), their usual chances of dozing off or falling asleep while engaged in 8 different activities. The total score is the sum of the 8 item scores, with scores ranging from 0 (no daytime sleepiness) to 24 (high sleep propensity in daily life). The ESS will be administered on Day 1 (Baseline), Day 7, and Day 14 of each treatment period. Descriptive statistics of total scores and change from baseline will be reported. Additionally, a mixed model will be used to evaluate the treatment effect. The model will include change from baseline as the dependent variable, fixed effects for baseline, treatment sequence, period, timepoint (i.e., Day 7, Day 14), disease type, and treatment, and a random subject effect. LS mean, LS mean difference, and LS mean difference p-value will be reported.

ESS data, including responses to individual questions, will be provided in a listing.

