2.3. Secondary Endpoints

The secondary endpoints will compare the effect of CST-103 co-administered CST-107 with that of placebo on the following:

1. Verbal fluency test (alphabet & category) CANTAB cognitive assessments, which include the following:
 - Reaction Time (RTI)
 - Rapid Visual Information Processing (RVP)
 - Verbal Recognition Memory (VRM) Phase I
 - Adaptive Tracking Task (ATT)
 - Paired Associates Learning Task (PAL)
 - Stop Signal Task (SST)
 - Delayed Verbal Recall
2. Digital wearable device (BioStamp) data, which includes four key measures of interest:
 - a. Activity and posture classifications, durations, and temporal patterns
 - b. Sleep (duration, posture transitions, and activity counts)
 - c. Autonomic function – heart rate variability (HRV)
 - d. Temporal pedometry (daily step count, and gait cadence)
3. Assessment of sleep using digital device and Epworth Sleepiness Scale (ESS)
4. Change in pupillary diameter as measured using the pupillary light reflex test
5. Geriatric Depression Scale (GDS), Hospital Anxiety and Depression Scale (HADS)
6. Adverse events (AE), electrocardiograms (ECGs), vital signs, laboratory safety tests (hematology, chemistry and urinalysis).
7. Plasma PK parameters of CST-103 and CST-107 (including C_{max} , t_{max} , AUC_t , AUC_{inf} , $t_{1/2}$)

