#### *Activity Tracking (AUS/NZ Subjects Only)*

The BioStamp nPoint device will be worn continuously for the 7 days prior to the Treatment Period 1 through the Day 1 visit (Baseline period), and re-dispensed at each of the Day 1 Visits in both periods, worn for 14 days, and removed on Day 14. During each of the three periods in which the subject wears the device, the device calculates 49 cumulative metrics for each day worn within the period. The metrics are then aggregated by study period (Baseline period, Treatment Period 1, Treatment Period 2). The 7 metrics related to activity tracking/classification are:

- Percent Wake Time defined as the percentage of sensor wear time spent awake. All time not spent awake is time spent asleep (identified in the raw data as `wake_percent`).
- Percent Moving Time defined as the percentage of waking time spent moving (sum of walking and other) (identified in the raw data as `moving_percent`).
- Percent Moving Other Time defined as the percentage of time spent moving but not walking (identified in the raw data as `moving_other_percent`).
- Percent Walking Time defined as the percentage of time spent walking

Sponsor: CuraSen Therapeutics, Inc.  
Protocol Number: CST103/CST107-CLIN-011  
Version and Date: [REDACTED] v1.0 / 24May2022

- Moving Activity Count defined as the activity counts per hour during moving periods (identified in the raw data as activity\_moving).
- Resting Activity Count defined as the activity counts per hour during resting periods
- Wake Activity Count defined as the activity counts per hour during moving and resting periods (identified in the raw data as activity\_resting).

All BioStamp aggregated data will be listed.

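### SAP 8.2 gives the named secondary endpoint daily step count no summary or model; Step Count Rate, as defined, is gait cadence in other units

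*SAP*

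**What the plan says.** Protocol 2.3 lists, among the wearable-device secondary endpoints, "Temporal pedometry (daily step count, and gait cadence". The endpoint table in SAP 3 repeats the pair, and the opening of the BioStamp text in SAP 8.2 says the device follows "temporal pedometry via daily step count and gait cadence". Protocol 8.8.1 commits to summarising BioStamp values and, where applicable, their changes from baseline.

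The metric list in SAP 8.2 then gives two pedometry items:

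- "Average Gait Cadence as defined as steps per minute during walking"
- "Step Count Rate as defined as step counts per hour during periods classified as walking", mapped to the raw variable `step_count_rate`.

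Given at least 5 days of wear in each period, "the metrics will be aggregated for each period to obtain a single value"; no averaging or weighting rule is stated. The SAP then plans "Descriptive statistics of the 17 metrics noted above" and of the 7 activity metrics from SAP 8.1. For all of these it plans a mixed model on change from the baseline period, with the baseline value, sequence, period, disease type and treatment as fixed effects and subject as a random effect, and it reports p-values.

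SAP 8.1 promises a listing of all aggregated BioStamp data. SAP 2.1, which records changes from the protocol, does not mention step count.

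**The concern.** Daily step count measures how much a subject walks. Cadence measures how fast the steps come while the subject is walking. A metric with walking time in the denominator can only speak to the second. Both analysed pedometry metrics have that denominator, so the plan followed literally reports cadence twice and leaves out the volume measure that the protocol named.

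Two things are at stake. A named secondary endpoint would reach the study report with at most a listing, and with no declared change. And with no multiplicity adjustment planned (SAP 5.3), a chance cadence result would produce two p-values that agree because they come from one quantity.

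**Working it through.** **1. The plan's own figure.** SAP 8.2 states 17 metrics. The list under it gives posture 5 + sleep 3 + heart rate variability 8 + pedometry 2 = 18. With the 7 activity metrics the total is 25, against 17 + 7 = 24 implied by the text. The figure does not reproduce, and nothing says which item, if any, is left out. None of the 25 is a count of steps per day. SAP 8.2 also says the device computes 29 daily metrics in these domains, so 29 − 18 = 11 are not itemised. A daily step count could be among them, but it would then only be listed.

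**2. The two definitions.** Let S be steps taken while walking and M the minutes spent walking.

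- Average Gait Cadence = S / M
- Step Count Rate = S / (M / 60) = 60 × S / M = 60 × cadence

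This is exact if both metrics use the same walking periods and the same aggregation over days.

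**3. Effect on the model.** Multiplying an outcome and its baseline covariate by 60 multiplies the treatment estimate and its standard error by 60. The t statistic and p-value do not move.

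**4. Numerical check on simulated data.** Assumptions: 30 subjects, 7 baseline days and 14 days per treatment period, walking time 30% higher on active treatment, no effect on cadence, and the SAP 8.2 model.

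| Outcome | Treatment estimate | t | p |
|---|---|---|---|
| Cadence, mean of daily values | −0.4433 steps/min | −0.566 | 0.571 |
| Step Count Rate, mean of daily values | −26.5983 steps/h | −0.566 | 0.571 |
| Step Count Rate, total steps / total walking hours | −19.7815 steps/h | −0.41 | 0.68 |
| Daily step count | +2,339 steps | 5.77 | <0.0001 |

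The first two rows agree by construction (−0.4433 × 60 = −26.598). The third shows what another aggregation rule does: the correlation with cadence was 0.999, so it remains a near-duplicate. The run gave a warning that a fit may lie on the boundary of the parameter space. The check confirms the algebra and says nothing about what the device actually outputs.

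**5. Illustration.** Assume 16 waking hours (960 minutes) and a cadence of 100 steps per minute.

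| | Walking 5% of waking time | Walking 7.5% |
|---|---|---|
| Walking minutes | 960 × 0.05 = 48 | 960 × 0.075 = 72 |
| Daily step count | 48 × 100 = 4,800 | 72 × 100 = 7,200 (+50%) |
| Average Gait Cadence | 100/min | 100/min |
| Step Count Rate as defined | 6,000/h | 6,000/h |
| Percent Walking Time (of waking time) | 5% | 7.5% |

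The two pedometry metrics do not move. Percent Walking Time, one of the 7 activity metrics put through the same model, does.

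**The case against.** **Other metrics see more walking.** A reader might infer that extra walking would go undetected, or that the secondary objective on movement is left unanswered. The documents do not support that. Percent Walking Time, Percent Moving Time and the activity counts in SAP 8.1 get the same summaries and the same model, in both cohorts. In the illustration Percent Walking Time rises by half. This stands, and it limits the consequence. It does not replace the endpoint: a share of time is not a step count, and the SAP plans no derivation of one from the other.

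**It may be a wording slip.** A reader might take it as established that the device variable has a walking-time denominator. The documents give only the SAP's description, and nearby labels are unreliable: Wake Activity Count is mapped to `activity_resting`, and a heart rate variability item labelled walking is mapped to `hrv_rmssd_wake`. If `step_count_rate` is really per hour of wear or waking time, it carries volume information and the duplication disappears. This stands, and it is why the fix begins with a check. In that case the written definition is still wrong.

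**The factor of 60 needs equal aggregation.** True; the SAP gives no rule. Otherwise the definitions describe near-duplicates.

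**Resting and moving time.** A reader might extend the duplication argument to "Percent Resting Time defined as the percentage of waking time spent resting" and "Percent Moving Time defined as the percentage of waking time spent moving". They probably sum to 100%, but the SAP does not say so, as it does for wake versus sleep and upright versus leaning. Showing both in a descriptive study biases nothing. Dropping one is a matter of taste and not part of this point.

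**The setting is exploratory.** There is no formal hypothesis testing, the device data come from Australia and New Zealand only, and two rows under one pedometry heading are unlikely to be read as independent confirmation. That argues for modest weight, not for leaving the mismatch in place.

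**Conclusion.** The point holds on the text as written. Daily step count is named in the protocol, in SAP 3 and at the start of the BioStamp text in SAP 8.2. No itemised metric counts steps per day, and SAP 2.1 does not declare a change. Step Count Rate as defined adds nothing to cadence: it is exactly 60 times cadence under equal aggregation, and it correlated at 0.999 under the alternative tried in the simulation.

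The loss is one of the two pedometry components of one secondary device endpoint, in one region of an exploratory study. It is not a loss of all information on walking volume, because Percent Walking Time is modelled. The conclusion assumes that the SAP definition would be programmed literally; whether it describes the device variable correctly cannot be decided from these documents. Either the endpoint is missing from the analysis or the definition is wrong, and both call for a correction. The 17 versus 18 count is clerical.

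**What to change.** Before database lock:

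1. Look up `step_count_rate` in the device data dictionary and establish its denominator.
2. If the denominator is walking time, replace Step Count Rate in SAP 8.2 with daily step count: total steps per valid day, or steps per hour of sensor wear to allow for differing wear time, averaged over each period. State what makes a day valid. Use the mixed model already specified, and keep Average Gait Cadence.
3. If the denominator is wear or waking time, correct the definition in SAP 8.2.
4. If the analysed measure still differs from daily step count, record that in SAP 2.1.
5. Change the metric count from 17 to 18, or to the number that results from the edit.

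The cost is a data dictionary query, a few lines of SAP text and at most one derived variable. Protocol 5.3.12 says the device already records step count, so no new data are needed.
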